1.0 SYNOPSIS

Title:	Prospective evaluation comparing the effects of constant current versus constant voltage in Deep Brain Stimulation using hybrid systems*.
Acronym:	PREFERENCE-H
Purpose:	To evaluate subject's preference for different stimulation modes (i.e. constant voltage and constant current).
Primary Objective:	The primary objective of the study is to demonstrate the subject's preference for a stimulation modality.
Secondary Objective:	The secondary objective of the study is to demonstrate the safety of the hybrid DBS system.
Primary Endpoint:	The primary endpoint is the proportion of subjects who indicate preference on constant current over constant voltage at the 3 Month follow-up visit.
Secondary Endpoint:	The secondary endpoint is the rate of safety events related to battery replacement procedures for hybrid systems.
Descriptive Endpoints:	
• The change in Speech Handicap Index at 3 and 12 Months compared to Baseline;• The change in total UPDRS score and the individual UPDRS components at 3 and 12 Months compared to Baseline;• The change in Levodopa medication at 3 and 12 Months compared to Baseline;• The change in Freezing of Gait Questionnaire (FOGQ) scores at 3 and 12 Months compared to Baseline;• The change in Tinetti Test scores at 3 and 12 Months compared to Baseline;• The change in Berg Balance Scale scores at 3 and 12 Months compared to Baseline;• The change in PDQ-39 scores at 3 and 12 Months compared to Baseline;• Proportion of subjects who indicate satisfaction with constant current at 3 and 12 Months;• Proportion of caregivers who indicate satisfaction with constant current at 3 and 12 Months;• Proportion of subjects who indicate preference on the constant current over the constant voltage at the 12 Month follow-up visit;• Summary of Health Economic Data for constant current compared to constant voltage.
Design:	Prospective, multicenter, multinational, post-market clinical study. The clinical study will be conducted in approximately 20 centers in Europe, Australia and the United States and approx. 170 subjects will be enrolled. Subjects will be followed for 12 months post battery replacement. The total duration of the study for a subject is expected to be approximately 15-24 months.

Clinical Investigational Plan

Devices used:	
• St Jude Medical Infinity™ DBS system• St Jude Medical Brio™ DBS system
Study Population	Subjects who have a diagnosis matching the approved indication and are being considered for an IPG replacement comprise the target population of this study. All subjects who meet the inclusion and none of the exclusion criteria and have signed an Ethics Committee (EC) or Institutional Review Board (IRB) approved informed consent will be considered enrolled in the study.
Inclusion/Exclusion Criteria	
Inclusion Criteria: Subjects meeting all the inclusion criteria can be considered for inclusion in the study:
 
• Subject signed the approved Informed Consent;• Subject is ≥ 18 and ≤ 74 years of age;• Subject is bilaterally treated with deep brain stimulation (DBS) in the subthalamic nucleus (STN) using a constant voltage device (i.e. Soletra™, Itrel™, Kinetra™, ActivaPC™ or ActivaRC™ IPG) and in the Investigator's opinion, is responding satisfactory to CV stimulation;• In the physician's opinion the subject is a suitable candidate for an IPG replacement with different stimulation paradigm;• Subject needs and/or requests an IPG replacement within 12 months after consent and the current IPG has at least 2.6 V output left (i.e. approx. 30% of full battery capacity) at the time of subject enrollment;• PD symptom onset is no longer than 20 years;• Subject has a Hoehn & Yahr score $<IV$ (on stim);• Subject with a normal cognitive function (MMSE ≥ 25);• Subject is fluent speaker (as judged by the investigator) of the language spoken in the country where the investigational site is located. 
Exclusion Criteria : Subjects will be excluded from the study if they meet any of the following criteria:
 
• IPG battery has less than 30% battery life at the time of consent;• Need to replace or reposition the leads or extensions during the IPG replacement procedure;• Subject had >10 recurrent falls experienced in the 3 months prior to consent;• Subject is unwilling to change to either a St Jude Medical Infinity™ or a St Jude Medical Brio™ DBS system for the IPG replacement;• Subject is unable to attend the study visits.
Data Collection	
Data will be collected at Enrollment, Baseline, IPG replacement, 3 Months and 12 Months after IPG replacement.
 
At the Enrollment Visit the Informed Consent procedure will be completed, Inclusion and Exclusion Criteria confirmed, Demographic and Medical History data collected.
 
At the Baseline Visit the following will be collected: Stimulation

Clinical Investigational Plan

Programming Settings, Medication, Health Economic Data, Speech Handicap Index, Freezing of Gait Questionnaire, Tinetti Test, Berg Balance Scale, Parkinson's Disease Questionnaire, Unified Parkinson's Disease Rating Scale (Part I, II IV On Med/OnStim, Part III On Med/On Stim and On Med/Off Stim), Satisfaction of Therapy Questionnaire for the subject and the caregiver, Adverse Events or Withdrawal (if applicable)

At the IPG Replacement Visit the implanted Medtronic® IPG will be explanted and replaced by a SJM Infinity™ DBS IPG or a SJM Brio™ DBS system according to the standard surgical procedures and instructions for use. The time point for the replacement will be decided by the physician according to their standard procedure. Intra-operative assessments and the initial CC programming session will be performed according to each individual site's standard procedure. The frequency, pulse width and number of contacts (monopolar/bipolar) of the stimulation should be kept constant between the constant voltage and the constant current stimulation. The following data will be collected: Implant Information, Initial Programming Information, Adverse Events or Withdrawal (if applicable)

At the 3 Months Visit the following will be collected: Stimulation Programming Settings, Medication, Speech Handicap Index, Freezing of Gait Questionnaire, Tinetti Test, Berg Balance Scale, Parkinson's Disease Questionnaire, Unified Parkinson's Disease Rating Scale (Part I, II, IV On Med/OnStim, Part III On Med/On Stim and On Med/Off Stim), Satisfaction of Therapy Questionnaire for the subject and the caregiver, Subject's Preference, Adverse Events or Withdrawal (if applicable)

At the 12 Months Visit the following will be collected: Stimulation Programming Settings, Medication, Speech Handicap Index, Freezing of Gait Questionnaire, Tinetti Test, Berg Balance Scale, Parkinson's Disease Questionnaire, Unified Parkinson's Disease Rating Scale (Part I, II, IV On Med/OnStim, Part III On Med/On Stim and On Med/Off Stim), Satisfaction of Therapy Questionnaire for the subject and the caregiver, Health Economic Data, Subject's Preference, Adverse Events or Withdrawal (if applicable).

*Hybrid systems are systems that use device components from different manufacturers (e.g. St Jude Medical and Medtronic).

Clinical Investigational Plan

1.1 STUDY FLOW CHART

1.2 STUDY CONTACTS

Clinical Investigational Plan

2.0 BACKGROUND AND JUSTIFICATION FOR CLINICAL STUDY

Deep brain stimulation (DBS) is widely used to treat motor symptoms in patients with advanced Parkinson's disease (PD) (Aström, Stereotact Funct Neurosurg 2010). DBS is the surgical treatment of choice for Parkinson's disease (PD) patients with medication resistant motor fluctuations, dyskinesias and refractory tremor (Krack, N Engl J Med. 2003; Lang, Mov Disord. 2006; Lang, Mov Disord. 2002) DBS of the subthalamic nucleus (STN) has been shown to improve not only the primary motor symptoms of PD and levodopa-induced motor complications, but also overall quality of life. DBS is an adjustable treatment, with the potential to optimize the treatment through implantable pulse generator (IPG) programming options, by changing the polarity, amplitude (V or mA), pulse width (μsec), and frequency (Hz) of the device.

As problematic side effects after initiation of DBS therapy with first generation unregulated DBS devices have included difficulties in speech, gait and some features of cognition (C Daniels, Movement Disorders 2010; Krack; N Engl Med. 2003). It has been shown that DBS treatment in the Subthalamic Nucleus (STN) can affect some aspects of intelligibility of speech depending on different IPG programming parameters. A particular cognitive side-effect most frequently observed after surgery can be a decline in the verbal fluency tasks in both the phonemic and semantic domain (Castelli, J Neurology 2007). Parameter settings shown to induce significant reduction of PD symptoms may in some cases result in either uninfluenced or intelligibility of speech. (Törnqvist, Movement Disorder 2005). A hypothesis explaining the worsening effect of STN-DBS on speech indicates the decline is related to the influence of the stimulation (current spread) on sounding neural pathways and this system includes cognitive circuits (Tripoliti, Movement Disorders 2008; Woods Neuropsychology Review, 2002)

Large similarities between gait patterns and speech involvement in PD and their response to STN-DBS and levodopa treatment have been demonstrated. The walking cadence and speech index of velocity tend to be lower in patients and are not significantly improved by STN-DBS or levodopa (Cantiniaux J Neurol Neurosurg Psychiatry 2010).

DBS is widely performed using voltage-controlled devices, which were refined from those utilized in cardiac pacing (Cheung & Tagliati, 2010). Such electrical stimulation can be supplied to the brain either using a constant current or a constant voltage power source. A constant current source provides a consistent current to the tissue by adjusting the voltage in response to the tissues impedance. A constant voltage source adjusts the current in response to a change in impedance thereby maintaining the voltage constant. There is evidence that constant current stimulation may provide more accurate control of the electrical field spread produced by these devices through adjustments for the heterogeneity in tissue impedance (Lempka, 2010).

Published research investigating the influence of DBS on parkinsonian patient's speech, gait and cognition has been performed applying constant voltage implantable impulse generators (IPGs). Patients, previously implanted with constant voltage devices and re-implanted (at IPG end of life) with a Brio™ constant current system have reported post-operative improvements in speech according to the feedback received from their implanting physicians.

This post-marketing evaluation has been designed to consistently investigate the subject's preference when switching from a Medtronic® constant voltage or constant current device to a St Jude Medical Infinity™ or St Jude Medical Brio™ constant current system. As electrodes will not be re-positioned,

Clinical Investigational Plan

differences in subject's preference are to be explained by the difference in shape of the delivered pulse or waveform between the two systems.

3.0 RISKS AND BENEFITS OF THE CLINICAL STUDY

3.1 DESCRIPTION OF SUBJECT POPULATION

The subject population enrolled in this investigation will be comprised of male and female subjects. Subjects have to meet the specific eligibility criteria in order to participate in the study.

3.2 ANTICIPATED CLINICAL BENEFITS

If subjects agree to take part in this study, there may or may not be direct medical benefits to individual subjects. The scientific use of the data, gathered from this study, may help the researchers discover better ways of programming movement disorder subjects and improving quality of life.

3.3 ANTICIPATED ADVERSE EVENTS AND ADVERSE DEVICE EFFECTS

The replacement of a DBS IPG involves risks. In addition to those risks commonly associated with surgery, the following risks are also associated with implantation and / or use of the device:

Intracranial hemorrhage (which can lead to stroke, paralysis or death); subcutaneous hemorrhage or seroma; hematoma; cerebrospinal fluid leakage or cerebrospinal fluid abnormality; brain contusion; infection or inflammation; antibiotic anaphylaxis; skin disorder; edema; persistent pain at surgery site or IPG site; erosion; brachial plexus injury (nerves to chest, shoulder and arm); postoperative pain, stress, or discomfort; neuropathy (nerve degeneration); hemiparesis (muscular weakness or partial paralysis on one side of the body); ballism or hemiballism (uncontrollable movements on both or only one side of the body); confusion – transient, nocturnal or ongoing; cognitive impairment, including delirium, dementia, disorientation, psychosis and speech difficulties; aphasia; deep vein thrombosis; complications from anesthesia; phlebitis (vein inflammation); pulmonary embolism (sudden blood vessel obstruction); aborted procedures (air embolism, unable to find target, surgical complication, etc.); complications from unusual physiological variations in patients, including foreign body rejection phenomena; pneumonia, seizure or convulsions; paralysis (loss of motor function, inability to move); stroke and death.

Complications may occur leading in some cases to surgical revision or explant of the system.

Possible deep brain stimulation complications include, but are not limited to the following:

Device-related complications:

- Undesirable changes in stimulation related to cellular changes in tissue around the electrodes, changes in the electrode position, loose electrical connections, or lead fracture
- Loss of therapeutic benefit due to a change in electrode positions, loose electrical connections, or lead or extension fraction
- Initial jolt or tingling during stimulation; jolting or shocking sensations
- Infection
- Paresthesia
- Lead fracture, migration or dislodgement
- Misplaced lead
- Extension malfunction, fracture or disconnect
- Deep brain stimulation system failure or battery failure with the device
- Deep brain stimulation system malfunction or dislodgement
- Spontaneous turning on or off of the IPG

Clinical Investigational Plan

- Allergic or rejection response to implanted materials
- Persistent pain, tightness or redness at the incision sites or general pain
- General erosion or local skin erosion over the IPG
- Persistent pain, tightness, or discomfort around the implanted parts (e.g. along the extension path in the neck)
- Impaired wound healing (e.g. incision site drainage) or abscess formation
- Additional neurosurgical procedure to manage one of the above complications or to replace a malfunctioning component

Stimulation- related complications or other complications:

- Worsening of motor impairment and PD symptoms including dyskinesia, rigidity, akinesia or bradykinesia, myoclonus, motor fluctuations, abnormal gait or incoordination, ataxia, tremor and dysphasia
- Paresis, asthenia, hemiplegia or hemiparesis
- Dystonia
- Sensory disturbance or impairment including neuropathy, neuralgia, sensory deficit, headache, and hearing and visual disturbance
- Speech and language impairment including aphasia, dysphagia, dysarthria and hypophonia
- Cognitive impairment including attention deficit, disorientation, abnormal thinking, hallucinations, amnesia, delusions, dementia, inability to act or make decisions, physiakinesia, long term memory impairment, psychiatric disturbances, depression, irritability or fatigue, mania or hypomania, psychosis, aggression, emotional lability, sleep disturbance, anxiety, apathy, drowsiness, alteration of mentation, postural instability and disequilibrium
- Restless leg syndrome
- Supranuclear gaze palsy
- Hypersexuality or increased libido
- Decreased therapeutic response
- Urinary incontinence or retention
- Diarrhea or constipation
- Cardiac dysfunction (e.g. hypotension, heart rate changes, or syncope)
- Difficulty breathing
- Increased salivation
- Weight gain or loss
- Eye disorder including eye apraxia or blepharospasm
- Nausea or vomiting
- Sweating
- Fever
- Hiccups
- Cough
- Cramps
- Worsening existing medical conditions

3.4 RESIDUAL RISKS ASSOCIATED WITH THE DEVICE UNDER INVESTIGATION, AS IDENTIFIED IN THE RISK ANALYSIS REPORT

DBS refers to the electrical stimulation of structures deep within the brain. DBS is considered an effective treatment for PD and essential tremor that is reversible, and adaptable.

Clinical Investigational Plan

The targeted study population consists of subjects who have been previously implanted with a Medtronic® DBS device and re-implanted at the IPG's end of life with a St Jude Medical Infinity™ DBS or St Jude Medical Brio™ DBS constant current system. Subject's preference will be collected for the 2 stimulation modes (i.e. constant voltage and constant current).

Effects of the DBS with constant current as well as with a constant voltage device are considered safe, non-destructive and reversible. The frequency and severity of procedural risks and complications related to the replacement of a Medtronic® device (constant voltage or constant current) by an Infinity™ device or Brio™ device (constant current) are expected to be similar to those cited in the current literature.

3.5 RISKS ASSOCIATED WITH PARTICIPATION IN THE CLINICAL STUDY

There are no study related additional risks expected within this study.

3.6 POSSIBLE INTERACTIONS WITH CONCOMITANT MEDICAL TREATMENTS AND/OR CONCURRENT MEDICAL INTERVENTIONS

There are no known possible interactions with concomitant medical treatments. The following procedures are contra-indicated for patients that have been implanted with this device:

- Diathermy (short-wave diathermy, microwave diathermy, or therapeutic ultrasound diathermy)
- MR imaging is contra-indicated for patients with an implanted neurostimulation system.

Please refer to the Infinity™ and Brio™ IPG Clinician manual/instructions for use regarding warnings and precautions.

3.7 STEPS THAT WILL BE TAKEN TO CONTROL OR MITIGATE THE RISKS

There are no study related additional risks expected within this study.

3.8 RISK-TO-BENEFIT RATIONALE

There are no additional risks for the subjects expected in this study.

3.9 DESCRIPTION OF HISTORY OF MODIFICATIONS OR RECALL IN RELATION TO SAFETY AND CLINICAL PERFORMANCE FOR DEVICE UNDER INVESTIGATION

This is a newly approved device and no device modifications have been reported to date. No device recalls have been issued concerning this product.

4.0 STUDY DESIGN

4.1 PURPOSE

The purpose of this clinical study is to evaluate subject's preference for different stimulation modes (i.e. constant voltage and constant current).

4.2 STUDY DESIGN AND SCOPE

This post-marketing evaluation has been designed to consistently investigate the subject's preference when switching from a Medtronic® device (constant voltage) to a St Jude Medical Infinity™ device or a St Jude Medical Brio™ DBS system (constant current system). As electrodes are not re-positioned, differences in subject's preference are to be explained by the difference in shape of the delivered pulse or waveform between the two systems.

Clinical Investigational Plan

This is the first known study to evaluate the effects of constant voltage versus constant current between 2 manufacturers in PD subjects with regards to subject's preference and symptom control.

Subjects currently implanted with a Medtronic® device, who have been recommended as a candidate for IPG replacement by the Investigator and meet the standard requirements will be approached to participate in the study. Each subject will be screened according to the inclusion/exclusion criteria. If the subject meets the study inclusion criteria and none of the exclusion criteria, he/she will be informed about the study to determine if he/she is interested in participating. After the subject signs the informed consent, he/she is considered enrolled in the study. The IPG replacement will be done according to the routine time point for IPG replacements.

During the surgery, the leads and extensions will not be re-positioned/revised. The IPG will be implanted according to the physician's standard operating procedures. The IPG will be activated and programmed using the Clinician Programmer by trained personnel. The subject may be given a Patient Controller, dependent on the physician's recommendation for patient care. Subjects will return for evaluation at 3 and 12 months post-implant for follow-up visits. This study is for data collection purposes and there are no additional risks to subjects that participate in this study than those risks associated with deep brain IPG replacement.

The study will be conducted in approximately 20 centers in Europe, Australia and the United States.

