4.5.1 Inclusion Criteria

- Subject (and caregiver, if applicable) signed the approved Informed Consent;
- Subject is ≥ 18 and ≤ 74 years of age;
- Subject is bilaterally treated with deep brain stimulation (DBS) in the subthalamic nucleus (STN) using a constant voltage device (i.e. Soletra™, Itrel™, Kinetra™, ActivaPC™ or ActivaRC™ IPG) and is responding satisfactory to CV stimulation in the Investigators opinion;
- In the physician's opinion, the subject is a suitable candidate for an IPG replacement with different stimulation paradigm;
- Subject needs and/or requests an IPG replacement within 12 months after consent and the current IPG has at least 2.6 V output left (i.e. approx. 30% of full battery capacity) at the time of subject enrollment;
- PD symptom onset is no longer than 20 years;

Clinical Investigational Plan

- Subject has a Hoehn & Yahr score <IV (on stim);
- Subject with a normal cognitive function (MMSE ≥25);
- Subject is fluent speaker (as judged by the investigator) of the language spoken in the country where the investigational site is located.

Subjects are not eligible for clinical study participation if they meet any of the following exclusion criteria:

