5.0 DEVICE UNDER INVESTIGATION AND CONTROL/COMPARATORS

5.1 DEVICE DESCRIPTION

In this study, the commercial available Infinity™ IPG with compatible header, the Brio™ IPG and the pocket adapter that are compatible with the Medtronic® extensions will be used in this study.

The IPG connects to the implanted extensions, which connect to the leads implanted in the brain. The IPG delivers electrical pulses through the extensions and leads to electrodes at a selected target in the brain in order to provide therapeutic stimulation. Physicians use the clinician programmer to create and modify a program for a patient. Subjects use the patient controller to control their prescribed programs. The patient magnet can turn the IPG on and off if the physician enables this functionality.

The Infinity™ IPG is an electronic device designed to be connected to one or two extensions. It is powered by a hermetically sealed battery within a titanium case and uses microelectronic circuitry to generate constant current electrical stimulation. The IPG is conductive on all sides, which allows the IPG case (also called 'can') to be used as an anode for monopolar stimulation. The IPG communicates wirelessly with system programmers and controllers, and IPGs are available in small and large sizes to accommodate different power needs. The IPG can receive software upgrades after implantation to provide patients with additional features as approved by the respective regulatory agencies. The models to be used in this study contain a header that is designed to allow the IPG to connect to Medtronic® extensions and/or leads that meet the compatibility guidelines.

The clinician programmer Application is a software application running on an iPad which is used by a clinician to wirelessly connect to Infinity™ IPGs to establish or modify the stimulation settings for a subject.

The patient controller is an off-the-shelf touch screen device (iPod Touch) with a SJM designed mobile Application software. Subjects use the patient controller to control their prescribed programs.

Description of the devices and instructions for use can be found in the User's Manual.

The components of the Brio™ DBS IPG to be used in this study include Brio™ DBS rechargeable IPG, a Pocket Adaptor™, a trial stimulator, a clinician programmer and a patient controller.

Description of the devices and instructions for use can be found in the User's Manual.

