6.5 IPG REPLACEMENT VISIT & PROGRAMMING

The implanted Medtronic® IPG will be explanted and replaced by a SJM Infinity™ DBS IPG or a SJM Brio™ DBS system according to the standard surgical procedures and instructions for use. The time point for the replacement will be decided by the physician according to their standard procedure.

Intra-operative assessments and the initial CC programming session will be performed according to each individual site's standard procedure.

The frequency, pulse width and number of contacts (monopolar/bipolar) of the stimulation should be kept constant between the constant voltage and the constant current stimulation.

Additional programming sessions may be required to optimize the therapy.

The following data will be collected:

- Implant information
- Initial programming information
- Adverse Events or Withdrawal (if applicable)

6.6 3 MONTH FOLLOW UP VISIT (3 months +/- 30 days after IPG replacement)

The current programming settings will be recorded before the questionnaires and tests.

The following data will be collected:

- Subject's Preference
- Speech Handicap Index (SHI)
- Unified Parkinson's Disease Rating Scale 'On Med/On Stim' ("On" state is defined as approximately 30 minutes after a subject takes anti-Parkinson medication when both the clinician and the subject indicate that the medication dose is effective.)
- Unified Parkinson's Disease Rating Scale part III 'On Med/Off Stim'
- Freezing of Gait Questionnaire (FOGQ)
- Tinetti Test
- Berg Balance Scale (BBS)
- Parkinson's Disease Questionnaire (PDQ-39)
- Satisfaction of Therapy Questionnaire for the subject
- Satisfaction of Therapy Questionnaire for the caregiver, if applicable
- Medication
- Adverse events or Withdrawal (if applicable)

After the questionnaires and the tests, the SJM Infinity™ or Brio™ DBS system parameters shall be optimized if needed. The optimized settings will be recorded.

6.7 12 MONTH FOLLOW UP VISIT (12 months +/- 30 days after IPG replacement)

This visit will also serve as the end-of-study assessment.

The current programming settings will be recorded before the questionnaires and tests.

Clinical Investigational Plan

The following data will be collected:

- Subject's Preference
- Unified Parkinson's Disease Rating Scale 'On Med/On Stim' ("On" state is defined as approximately 30 minutes after a subject takes anti-Parkinson medication when both the clinician and the subject indicate that the medication dose is effective.)

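### Unmoved electrodes do not leave waveform as the only explanation: the one-way switch supports preference for the replacement system as implanted and programmed, not for the waveform or stimulation mode alone

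*Combined protocol and SAP*

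**What the plan says.** Sections 2.0 and 4.2 both start from the fact that the electrodes will not be moved and conclude that "differences in subject's preference are to be explained by the difference in shape of the delivered pulse or waveform between the two systems". No other premise is given in that sentence. Section 4.2 also describes the study as the first known one to "evaluate the effects of constant voltage versus constant current between 2 manufacturers in PD subjects".

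The plan has real controls. Section 4.2 says leads and extensions are not revised at surgery, and section 4.5.2 excludes subjects who need that. Sections 1.0, 6.2 and 6.5 say that the "frequency, pulse width and number of contacts (monopolar/bipolar) of the stimulation should be kept constant" between the two modes.

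Other things are left open. Section 6.5 says "the initial CC programming session will be performed according to each individual site's standard procedure", and then: "Additional programming sessions may be required to optimize the therapy". Section 5.1 allows either the Infinity generator or the Brio, whose components include a "rechargeable IPG, a Pocket Adaptor". Section 4.4.3 lists change in levodopa as a descriptive endpoint.

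The purpose (1.0, 4.1), primary objective (1.0, 4.3.1) and primary endpoint (1.0, 4.4.1) are worded as a preference between stimulation modes. Section 6.11 asserts that the design and the selection criteria deal with every foreseeable factor that could compromise the outcome; it names none.

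**The concern.** Fixing the electrodes rules out lead position as a reason for a changed experience. It does not rule out the other things that change in the same operation or in the weeks after it. The sentence in 2.0 and 4.2 treats the first as if it were the second.

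What is at stake is the reading of the primary result. The objective and endpoint are already phrased in terms of mode, so a majority in either direction could be reported as evidence about constant current, or about waveform, on the authority of the plan's own rationale. Section 6.11, where a reader would look for the caveat, says that none is needed.

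**Working it through.** There is no figure in the plan to reproduce. The enrollment and analysis targets in section 12.2 (170 and 115) play no part, and no section gives the size of a non-waveform influence. The check is to set the plan's procedures beside its inference.

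1. **Order and comparator.** Under section 6.5 the old generator is explanted and the new one implanted. Every subject goes from constant voltage to constant current. The visible text describes no concurrent control, blinding, reverse order or return to constant voltage. Preference is asked at 3 and 12 months (section 6.2, Table 1), both times after the switch. The primary question comes 3 months +/- 30 days after the old device was removed, so it compares a current state with a remembered one.

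2. **Held across the switch.** Leads, extensions, frequency, pulse width and number of contacts. These remove several competing explanations and deserve credit.

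3. **Changes with the mode.** Manufacturer and generator hardware. The hardware includes the battery, a rechargeable unit and pocket adaptor where Brio is used (5.1), and possibly a patient controller, given on the physician's recommendation (4.2). These are aspects of one act, replacing the generator, and should not be tallied as separate influences.

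4. **Not on the keep-constant list.** Amplitude, which section 2.0 names as a programming option in V or mA, and the choice of active contacts (only their number is listed). Both belong to programming, which is site-specific at the start and open to optimisation before the 3-month visit.

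5. **Ambiguous items.**
   - *Medication* may change, since its change is measured. A change could compete with mode as a cause of preference, or could follow from the mode.
   - *Old battery.* Section 3.4 describes subjects "re-implanted at the IPG's end of life", while section 4.5.1 requires that "the current IPG has at least 2.6 V output left", but at enrollment only. The need or request for replacement within 12 months of consent (4.5.1) and the 30% battery exclusion (4.5.2) limit depletion at the time of replacement without excluding it.

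6. **Why one proportion cannot separate these.** As an assumption for illustration only, let waveform have no effect, so that subjects who judge on waveform split evenly, and let a share *w* choose on other grounds.
   - If all of *w* favour the new system, the proportion is *w* + (1 - *w*) x 0.5. For *w* = 0.10 this is 0.10 + 0.45 = 0.55; for *w* = 0.20 it is 0.20 + 0.40 = 0.60.
   - If all of *w* favour the old system, it is (1 - *w*) x 0.5, which gives 0.45 and 0.40.
   - A proportion of 0.55 would equally arise from *w* = 0 and a true 55% preference on waveform.

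   The documents give no value for *w* and no direction, and nothing visible in the design estimates either. The illustration shows only that the data cannot tell these cases apart.

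**The case against.** The strongest reply has several parts.

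- **The plan already says that whole systems are compared.** The title refers to hybrid systems, and the sentence before the attribution in 4.2 describes switching from one manufacturer's constant-voltage device to another's constant-current system. This is true, but the next sentence then narrows the explanation to pulse shape or waveform, and the objective and endpoint speak of mode.
- **The sentence is rationale.** No visible hypothesis, analysis or decision rule uses it. This stands, and it is why the remedy is wording and not redesign.
- **Some reprogramming is inherent in changing mode.** This also stands. It is a reason to describe the effect as that of a system as programmed.
- **This is a post-market study at routine replacement.** The absence of blinding or switch-back is a design choice. A reader might infer that it is an error; the documents do not support that reading, and the point here concerns only the claim placed on the design.
- **Material is unseen.** The flow charts, the body of 12.1.1 and the case report form with the preference question are not available. The question may ask about stimulation, the device or therapy overall. That qualifies exactly what the proportion means. A narrowly worded question would still not by itself separate waveform from amplitude, contact choice or open-label expectation.

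A reader might also infer that the result is biased toward constant current. The documents do not show this: subjects must be responding satisfactorily to constant voltage (4.5.1), and those unwilling to change to the new systems are excluded (4.5.2). Neither rule settles a direction.

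**Conclusion.** The concern holds as a limit on interpretation. Fixed electrodes, even with frequency, pulse width and number of contacts also held, do not isolate waveform or stimulation mode in a one-way open switch between manufacturers. The 3-month proportion remains a valid description of preference for the replacement constant-current system, as implanted and programmed, over the previous constant-voltage system.

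Its size cannot be quantified: the documents give neither the magnitude nor the direction of any non-waveform influence. The number of things that change is not a measure of bias, and medication change should not be called a confounder outright. The conclusion rests on the visible text and on the assumption that the missing flow charts and the body of 12.1.1 do not describe a control, blinding or a return to constant voltage.

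Separately and of minor weight, sections 2.0 and 3.4 describe the old device as constant voltage or constant current, while 4.2 and 4.5.1 say constant voltage only. A reader might infer that constant-current to constant-current switches will enter the analysis. The inclusion criterion does not allow that, so this is an inconsistency of wording. It should be corrected.

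**What to change.** 1. **Sections 2.0 and 4.2.** Replace the attribution sentence with: *Preference is for the replacement constant-current system, as implanted and programmed, relative to the previous constant-voltage system; it cannot be attributed to waveform or stimulation mode alone.* Add the same limit on interpretation to the purpose, primary objective and primary endpoint (1.0, 4.1, 4.3.1, 4.4.1).
2. **Section 6.11.** Replace the statement that everything foreseeable is covered with a non-exhaustive one: *Factors not separated from stimulation mode in this design include manufacturer and IPG hardware (including battery and patient controller); amplitude, choice of contacts and programming; medication, which may be a cause or a consequence; and open-label expectation and recall of the removed device.*
3. **Minor.** Reconcile the description of the old device in 2.0 and 3.4 with that in 4.2 and 4.5.1.

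The cost is a wording amendment with a justification statement and notification to, or approval by, the IRB/EC and regulatory authorities where required (section 14.0), across about 20 centers. Endpoint calculation, visits, data collection and sample size do not change. The downside for the sponsor is a more modest claim.
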